Appendix 1. Study Visit Mapping for Pruritus NRS and Sleep-loss Diary and POEM

Pruritus NRS and sleep loss are collected as a daily diary; entries will be mapped to study week by the following:

Week	Start Day	End Day
Baseline	Date of First Injection ^a - 7	Date of First Injection-1
Week 2	Week 2 Visit Date - 7	Week 2 Visit Date - 1
Week 4	Week 4 Visit Date - 7	Week 4 Visit Date - 1
Week 6	Week 6 Visit Date - 7	Week 6 Visit Date - 1
Week 8	Week 8 Visit Date - 7	Week 8 Visit Date - 1
Week 10	Week 10 Visit Date - 7	Week 10 Visit Date - 1
Week 12	Week 12 Visit Date - 7	Week 12 Visit Date - 1
Week 14	Week 14 Visit Date - 7	Week 14 Visit Date - 1
Week 16	Week 16 Visit Date - 7	Week 16 Visit Date - 1
Week 20	Week 20 Visit Date - 7	Week 20 Visit Date - 1
Week 24	Week 24 Visit Date - 7	Week 24 Visit Date - 1
Week 28	Week 28 Visit Date - 7	Week 28 Visit Date - 1
Week 32	Week 32 Visit Date - 7	Week 32 Visit Date - 1
Week 36	Week 36 Visit Date - 7	Week 36 Visit Date - 1
Week 40	Week 40 Visit Date - 7	Week 40 Visit Date - 1
Week 44	Week 44 Visit Date - 7	Week 44 Visit Date - 1
Week 48	Week 48 Visit Date - 7	Week 48 Visit Date - 1
Week 52	Week 52 Visit Date - 7	Week 52 Visit Date - 1

^a If date of first injection is missing, the randomization date will be used.

If multiple assessments on a single day are present, use the first assessment. If an assessment could be mapped to different weeks, it will be mapped to the earlier week. Derivation of the weekly mean

This document is confidential.

scores for Pruritus NRS and Sleep-loss could be found in the table in the section 9.2. Definitions for Efficacy Endpoints. If at least 1 of the 7 days contains non-missing daily assessments, post-baseline weekly score will be calculated using prorated weekly average. If the range of 7 days are all missing daily assessments, then the weekly score is missing.

POEM are collected every week via eDiary, the visit week mapping will follow the following rule: the last collected POEM data before the visit date would be used, the evaluation window is injection date - 7 to injection date -1 for baseline and assessment date - 7 to assessment date -1 for post-baseline. For example, if a patient gets an injection/assessment on the 14th, we would use the scale completed in between the 13th and the 7th.

This document is confidential.

Appendix 2. Details of Combining Estimates and Test Statistics for Categorical Endpoints with Multiple Imputation

Following the implementation of MCMC-MI imputation as specified in Section エラー! 参照元が見つかりません。, the data sets with imputations should be set together and sorted by imputation number. The following sections describe the processes for combining inferences for the individual imputed data sets into one inference for reporting. All calculations are performed in SAS software version 9.4 or higher.

Summarize Unadjusted Response Rate

The response rates, overall and by treatment arm, and their associated standard errors (SE) are computed for each imputed data set using PROC FREQ with the *riskdiff* option specified for the appropriate column in the TABLES statement. The response rates and SEs from the resulting output are combined across the imputed data sets using PROC MIANALYZE, separately for each arm and the overall group.

Note that the estimate and 95% confidence interval (CI) bounds output by PROC MIANALYZE are percents (i.e., they are in terms of the response rate). To obtain the number of responders, the estimated percentage is multiplied by the number of individuals in the analysis population and rounded to the nearest integer.

Compute Stratified Measures of Association

The common risk difference, common odds ratio (OR), and Cochran-Mantel-Haenszel (CMH) test statistic are computed for each imputed data set using PROC FREQ with the *riskdiff* option for the appropriate column (for risk difference) and the *cmh* option (for odds ratio and CMH test statistic) specified in the TABLES statement. Each of these analyses are stratified by geographic region, age group, and baseline disease severity via inclusion of these variables in the TABLES statement with the treatment and outcome variables.

Note that the PROC FREQ output corresponding to the Mantel-Haenszel method is used for the risk difference, and the output corresponding to the General Association statistic is used for the CMH statistic. PROC MIANALYZE is then called separately for each of these measures, with further details in the sections below.

Common Risk Difference

No transformation is necessary before using PROC MIANALYZE to combine the risk difference estimates and their associated SEs across the imputed data sets. This procedure outputs an estimate of the common risk difference and the associated 95% CI bounds.

Common Odds Ratio

The OR from each imputed data set is first transformed using the natural logarithm. The SE for each log OR (SE_{logOR}) is derived from the OR 95% CI bounds (LB_{OR} , UB_{OR}) according to the following equation: $SE_{logOR} = (\ln(UB_{OR}) - \ln(LB_{OR}))/ (2 * 1.96)$. The log OR and derived SE are then combined using PROC MIANALYZE, which outputs a combined estimate of the log OR and the associated 95% CI. Finally, these measures can be exponentiated to transform them back to the OR scale.

This document is confidential.

Cochran-Mantel-Haenszel Test

The CMH test statistic (CMH) from each imputed data set is transformed using the Wilson-Hilferty transformation and standardized so that it has approximately a standard Normal distribution (Ratitch

2013). In particular, the transformed CMH statistic is computed as follows: $CMH_{WH} = \frac{\left(\frac{CMH}{df}\right)^{\frac{1}{2}} - (1 - \frac{2}{9+df})}{\sqrt{\frac{2}{9+df}}}$,

where df is the degrees of freedom of the CMH statistic. Then the SE for each CMH_{WH} is 1, and PROC MIANALYZE is used to output a combined estimate of the transformed CMH statistic. Note that the two-sided p-value output by PROC MIANALYZE is not used directly, but instead the one-sided p-value is computed manually using both the t statistic and two-sided p-value output by PROC MIANALYZE: if t statistic is greater than 0, then one-sided p-value is computed as half of the two-sided p-value; otherwise, the one-sided p-value is computed as 1 - half of the two-sided p-value. The resulting one-side p-value is reported as the pooled p-value for the CMH test.

This document is confidential.

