7.2.4 Rationale for Trial Assessments

The efficacy assessments conducted in this study include clinician's and patient's reported outcome that have been validated and extensively employed in patients with AD.^{4,41} The majority of assessments discussed below are also being employed in the other phase 3 trials of lebrikizumab. The frequency of assessments is deemed adequate to properly monitor development and achievement of response in terms of efficacy measures and QoL changes during the Induction Period, and the maintenance of a stable response over the Maintenance Period.

EASI, BSA, and IGA scores allow for evaluation of disease severity and extent as well as the physician's overall judgment at Screening and after study treatment. Achievement of EASI 75 response or IGA assessment of 0 or 1 are both response criteria used as primary or key secondary end points to confirm success of treatment in AD clinical trials. The SCORAD is a validated composite measure developed by the European Task Force of Atopic Dermatitis (ETFAD) that incorporates both objective physician's and subjective patient's assessments. POEM is a validated measure that uses patient-reported outcomes (PROs) specifically designed to measure AD severity from the patient's perspective.³⁸

All pruritus entries will be recorded daily in the patient's diary from Week 0 to Week 2, weekly from Week 2 to Week 16 of the Induction Period, and every 2 weeks during the Maintenance Period.

All skin pain and sleep loss entries will be recorded daily in the patient's diary from Week 0 to Week 2, weekly from Week 2 to Week 16 of the Induction Period, and every 4 weeks during the Maintenance Period.

The RECAP is a newly designed patient questionnaire designed to capture AD control as experienced by the patient.⁴²

QoL related to the patient's AD condition will be assessed by administration of the DLQI (adult or paediatric version [eg, the CDLQI] depending on the age of the patient), which is commonly used in AD clinical trials and often also in dermatology clinical practice.⁴³ The WHO-5 is a validated questionnaire measuring current positive mental well-being.⁴⁴ The scale has adequate validity both as a Screening tool for depression and as an outcome measure in clinical trials and has been widely used in clinical trials of any type of therapeutic indications. Depression has been associated with AD.⁴⁵

The TSQM-9 is a reliable and valid instrument to assess patients' satisfaction with medication.⁴⁶

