To evaluate the efficacy in patients not adequately controlled with cyclosporine or for whom cyclosporine is not medically advisable between Week 16 up to Week 52.	
- Percentage of patients achieving IGA 0/1 and 2-point improvement (by week, between Week 16 and Week 52).- Percentage of patients achieving a 4-point improvement Pruritus NRS (by week, between Week 16 and Week 52).- Percentage of patients achieving EASI 75, EASI 90, EASI 50 (by week, between Week 16 and Week 52)- Percentage of patients achieving a 4-point improvement in DLQI/CDLQI (by week, between Week 16 and Week 52).- Percentage of patients achieving a 4-point improvement Skin Pain NRS (by week, between Week 16 and Week 52).- Change from Baseline BSA (by week, between Week 16 and Week 52).- Change from Baseline SCORAD (by week, between Week 16 and Week 52).- Change from Baseline Pruritus NRS (by week, between Week 16 and Week 52).- Change from Baseline sleep loss (by week, between Week 16 and Week 52).- Change from Baseline POEM (by week, between Week 16 and Week 52).- Change from Baseline DLQI/CDLQI (by week, between Week 16 and Week 52).- Change from Baseline Skin Pain NRS (by week, between Week 16 and Week 52)- Proportion of TCS-free days from Baseline (by week, between Week 16 and Week 52)- Time to TCS-free use (days)
	Exploratory Endpoints: CCI
To evaluate the safety and tolerability of lebrikizumab in patients not adequately	Safety and Tolerability Endpoints

This document is confidential.

controlled with cyclosporine or for whom cyclosporine is not medically advisable up to Week 16	
 - TEAEs, Related SAEs, TEAEs leading to study treatment discontinuation, AESIs and Deaths. - Observed results and changes from Baseline in Laboratory Results (Haematology, Chemistry and Urinalysis) to Week 16. - Observed results and changes from Baseline in Vital Signs Results to Weeks 2, 4, 8, 12 and 16. - Percentage of patients with abnormalities in physical examination at Week 16.

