^d Visit window for patient-reported outcomes is -3 days during Induction Period and -5 days during Maintenance Period.

^e For adults, height should only be captured at screening. For adolescents, height should only be captured at screening and Week 52.

^f Patients should attend the visit fasted. Patients should not eat or drink anything except water for 8 hours before sample collection. Alcohol consumption will not be permitted for at least 8 hours before visits. Strenuous physical activity should be avoided for at least 8 hours before a visit.

^g The contraception check is to confirm that contraception, if required, is used consistently and correctly.

^h Serum Beta-hCG at Screening. Urine pregnancy test at all other identified visits. If required per local regulations and/or institutional guidelines, pregnancy testing can occur at other times during the study treatment period. For WOCBP, urine pregnancy tests will be conducted every 4 weeks after last dose of study medication (W54, W58, and W62) and at W68. Male subjects engaged in a relationship with a WOCBP must be contacted every 4 weeks after last dose of study medication (W54, W58, and W62) and at W68 to ensure respect of the contraception.

ⁱ Patient-reported outcomes and quality of life measurements should all be completed before other study assessments. Assessments/procedures should be conducted in the following order: 1) patient-reported outcomes; 2) investigator assessments and other efficacy assessments; 3) safety and laboratory assessments (including sample collection for biomarkers); and 4) administration of study drug. Completed eDiary entries for Pruritus NRS and sleep-loss scales are needed for a minimum of 4 out of 7 days in the week preceding randomisation visit.

^j To be performed daily up to W2, weekly from W2 to W16, and every 2 weeks from W16 onward.

^k To be performed daily up to W2, weekly from W2 to W16, and every 4 weeks from W16 onward.

^l For patients who consent at selected sites.

^m Compliance assessment for study drug, TCS, as well as accountability.

ⁿ Only applicable to patients who do not enter the Extension Period.

This document is confidential.

Only for German Extension according to Local Protocol Amendment 4 for Germany

Extension Period and Safety Follow-up Visit for Patients who Enter the Extension Period

Study Procedures	Extension Period						Safety Follow-up Visit ^a
	EXT 1 ^b	EXT 2	EXT 3	EXT 4 ^c	EXT 5 ^c	EXT 6 ^c	
Study Visit							

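### SAP Appendix 1 maps pruritus only 4-weekly after Week 16 although it is recorded 2-weekly, so 9 of 18 Maintenance time points drop out of the descriptive summaries without being declared

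*SAP*

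**What the plan says.** **Collection.** SAP Section 4.6, footnote j, gives the pruritus schedule: "To be performed daily up to W2, weekly from W2 to W16, and every 2 weeks from W16 onward". Footnote j of Protocol Table 1 says the same, and Protocol 7.2.4 repeats it: "weekly from Week 2 to Week 16 of the Induction Period, and every 2 weeks during the Maintenance Period". The Maintenance schedule has a visit every 2 weeks from Week 18 to Week 52, with pruritus marked at each. Sleep loss and skin pain follow footnote k: "To be performed daily up to W2, weekly from W2 to W16, and every 4 weeks from W16 onward".

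**Endpoints.** Protocol Table 3 defines 4-point pruritus improvement and change from baseline in pruritus by visit from Week 16 to Week 52. SAP Section 3 keeps both, by week.

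**Mapping.** SAP Appendix 1 opens: "Pruritus NRS and sleep loss are collected as a daily diary; entries will be mapped to study week by the following". Up to Week 16 it has a row for every 2-weekly visit. The first row after that starts at "Week 20 Visit Date - 7", and the remaining rows are 4 weeks apart. Every row ends on the day before the visit. A window with no entries gives no score: "If the range of 7 days are all missing daily assessments, then the weekly score is missing".

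**Declared changes.** SAP Section 11 renames by-visit analyses as by-week and adds two Induction endpoints. It mentions no reduction in pruritus time points.

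**The concern.** The table follows the sleep-loss schedule and is applied to pruritus as well. A programmer following it would have no row for Weeks 18, 22, 26, 30, 34, 38, 42, 46 and 50, although pruritus is scheduled at each of those visits. Two secondary endpoints that the protocol defines by visit would then be summarised at half of their post-Week-16 visits.

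Week 18 is among the missing weeks. It is the first scheduled pruritus value after placebo patients start lebrikizumab at Week 16, and the study is still double-blind at that visit. SAP Section 9.7 plans to repeat the Induction analyses descriptively for Maintenance. The Induction rows are 2-weekly, and the change of spacing is not explained.

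**Working it through.** The plan states no figure on this point, so the check is a count of the schedule followed by a test of the windows.

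**1. Time points**

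| Set | Weeks | Count |
|---|---|---|
| Recorded (SAP 4.6 footnote j) | 18, 20, 22, … 52 | (52 − 18)/2 + 1 = 18 |
| Mapped (Appendix 1 rows after Week 16) | 20, 24, 28, … 52 | (52 − 20)/4 + 1 = 9 |
| Not mapped | 18, 22, 26, 30, 34, 38, 42, 46, 50 | 18 − 9 = 9 |

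Share not mapped: 9/18 = 50%. With Week 16, which is mapped, the base is 19 and the share is 9/19 = 47%.

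**2. Do the unmapped entries fall in a neighbouring window?** The Maintenance window for patient-reported outcomes is −5 days (SAP 4.6 footnote d). Each Appendix 1 window runs from visit day − 7 to visit day − 1. With visits exactly on schedule:

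- entry 1 to 5 days before the visit: 9 of 18 entries fall in a window, all belonging to the nine listed weeks;
- entry on the visit day: 0 of 18 fall in a window.

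Now let visits drift. Let *a* be the shift of the unlisted visit, *b* the shift of the neighbouring listed visit (each −5 to +5 days), and *o* the lead of the entry before its own visit (0 to 5 days). There are 11 × 11 × 6 = 726 combinations. The next listed window opens 14 − 7 = 7 days after the unlisted visit's target day, so an entry reaches it only if *a* − *b* − *o* ≥ 7. That holds in 10 + 6 + 3 + 1 = 20 combinations (*o* = 0, 1, 2, 3), or 20/726 = 2.8% with equal weights. The preceding listed window closes 15 days before the target day, so it needs *a* − *b* − *o* ≤ −15, which only *a* = −5, *b* = +5, *o* = 5 meets. Drift therefore rescues almost nothing.

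**3. Entries involved.** 9 per completing patient × 312 randomised patients = 2,808. This is a ceiling that assumes no dropout.

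**4. Does another section supply the weeks?** SAP Section 7.4 deals with eCRF data and with the use of unscheduled assessments, and its printed windows stop at Week 14. SAP Section 9.2 defines the weekly mean without listing weeks. The Appendix 1 rule that prefers the earlier week settles entries that fit two windows; these fit none.

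**5. Effect of the fix.** With nine rows added and the present window, 18 of 18 time points are mapped for entries 1 to 5 days before the visit, but still 0 of 18 for visit-day entries. If the window ends on the visit day, leads of 0 to 5 days all lie inside it and 18 of 18 are mapped in both cases.

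**The case against.** The best defence is that the 4-weekly grid is deliberate. Weeks 20, 24, … 52 are also the Maintenance vital-signs weeks in the endpoint tables, and the EASI 50 discontinuation rule in Protocol 7.1 uses Weeks 24 to 48 of the same grid. Eight of the nine unmapped weeks are visits that may be remote; only Week 18 is not. Appendix 1 also leaves first-week daily entries unmapped, so collecting more often than summarising is not in itself an error. Under Protocol 11.2 the SAP prevails where the two differ, and a by-week endpoint need not mean every second week.

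This stands in part: a 4-weekly summary would be a legitimate choice. But the SAP does not say that it was chosen. Section 11 changes the label and not the number of time points, and the Appendix 1 description of both scales as a daily diary (pruritus and sleep loss are daily only up to Week 2) suggests that the table was not matched to the pruritus schedule.

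Three stronger readings are tempting and are not supported:

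- **That the endpoints cannot be produced or the data are lost.** Nine post-Week-16 summary points remain, and SAP Sections 7.1 and 9.4 keep the values in listings.
- **That the trial's inference is affected.** SAP Section 9.3 makes Maintenance efficacy descriptive and as observed. Weeks 2 to 16 have a row for every visit, so the missing rows do not touch the Week 16 key secondary pruritus analysis.
- **That Week 18 costs a blinded treatment comparison.** Both arms receive lebrikizumab from Week 16 and no between-arm test is planned after it. What is lost is a descriptive early value.

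**Conclusion.** The gap is real and its size is exact for on-schedule visits: 9 of the 18 scheduled pruritus time points from Week 18 to Week 52 have no mapped week. Two secondary endpoints are summarised at half of their post-Week-16 visits, contrary to the protocol's by-visit definition and without a declaration in SAP Section 11.

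The consequence is modest, because only descriptive Maintenance tables change. About 2,800 entries is an upper bound; discontinuations, including those under the EASI 50 rule, reduce it. That the other nine time points are captured assumes entries 1 to 5 days before the visit. Protocol 10.1 has patient-reported outcomes assessed at the start of the visit, and entries made that day would miss every window, including any new rows built on the same anchor. Where the Induction windows should end is a separate question, not assessed here.

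The sponsor should correct this before the Maintenance tables are programmed, because the rule as written would otherwise be followed.

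**What to change.** 1. Give pruritus its own post-Week-16 mapping in Appendix 1 by adding rows for Weeks 18, 22, 26, 30, 34, 38, 42, 46 and 50. Keep the 4-weekly table for sleep loss.
2. Extend the post-Week-16 window to include a pre-dose entry made on the visit day. Without this, the new rows may capture little.
3. Replace the daily-diary description with the actual frequencies: daily to Week 2, weekly to Week 16, then every 2 weeks for pruritus and every 4 weeks for sleep loss.
4. If a 4-weekly pruritus summary is intended, keep the present rows and declare it in SAP Section 11 as a change from the protocol. Items 2 and 3 still apply.

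The cost is nine table rows, a few sentences and longer descriptive tables. No new data, model or test is needed.

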- b. Visits shaded in blue may be conducted remotely or on-site, per preference of the study site or patient. W68 will be on-site for WOCBP only.
- c. For patients who received placebo during the Induction Period, loading doses of lebrikizumab will be given at W16 and W18 during the Maintenance Period. In order to maintain the double-blind, patients from the lebrikizumab 250 mg Q2W arm will be administered a second injection of blinded placebo during W16 and W18. From W20 onwards, all patients will receive 1 injection of lebrikizumab 250 mg Q2W.
- d. Visit window for patient-reported outcomes is -3 days during Induction Period and -5 days during Maintenance Period.
- e. For adults, height should only be captured at Screening. For adolescents, height should only be captured at Screening and Week 52.
- f. Patients should attend the visit fasted. Patients should not eat or drink anything except water for 8 hours before sample collection. Alcohol consumption will not be permitted for at least 8 hours before visits. Strenuous physical activity should be avoided for at least 8 hours before a visit.
- g. The contraception check is to confirm that contraception, if required, is used consistently and correctly.
- h. Serum beta-hCG at Screening. Urine pregnancy test at all other identified visits. If required per local regulations and/or institutional guidelines, pregnancy testing can occur at other times during the study treatment period. For WOCBP, urine pregnancy tests will be conducted every 4 weeks after last dose of study medication (W54, W58, and W62) and at W68. Male subjects engaged in a relationship with a WOCBP must be contacted every 4 weeks after last dose of study medication (W54, W58, and W62) and at W68 to ensure respect of the contraception.
- i. Patient-reported outcomes and quality of life measurements should all be completed before other study assessments. Assessments/procedures should be conducted in the following order: 1) patient-reported outcomes; 2) Investigator assessments and other efficacy assessments; 3) safety and laboratory assessments (including sample

collection for biomarkers); and 4) administration of study drug. Completed eDiary entries for Pruritus NRS and sleep-loss scales are needed for a minimum of 4 out of 7 days in the week preceding randomisation visit.

- j. To be performed daily up to W2, weekly from W2 to W16, and every 2 weeks from W16 onward.

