10.1 General Conditions of the Trial

Informed consent must be obtained before performing any procedure related to the trial. This can be done at any time before the Screening visit. ICF/IAF must be signed after the patient has received sufficient information about the trial and after he/she has had the opportunity to ask any questions and consider other treatment options. Participation in the trial must be documented in the patient's medical records and a copy of the ICF/IAF will be given to the patient.

Trial visits will be scheduled in the morning whenever possible. At the scheduled protocol visits, IMP dosing must occur while being witnessed by the research personnel at the clinic to ensure the proper IMP application, as well as the correct timing of activities to occur before and after dosing.

Trial visit dates must be scheduled with respect to the randomisation visit day. To adapt appointments to local holidays, patient's availability, or site internal organisation needs, a time window of ± 3 days is allowed for visits during the Screening Period, Induction Period, and a time window of ± 5 days is allowed for the SFU visit and visits during the Maintenance Period. PROs must be completed prior to other study-related activities. Therefore, the visit window for

PROs is -3 days during Induction Period and -5 days during Maintenance Period. Please contact the CRA or PPD Medical Monitor for advice in case of exceptional situations.

The study drug should be administered after all other procedures and assessments have been completed at applicable visits.

PROs will be assessed at the start of the visit before any other assessments or procedures. Assessments or procedures should be conducted in the following order: 1) PROs; 2) Investigator assessments and other efficacy assessments; 3) safety and laboratory assessments (including sample collection for biomarkers); and 4) administration of study drug.

Vital signs should be assessed before blood sampling.

Laboratory tests will be performed using the equipment provided by the Sponsor for trial purposes through a specialised provider, who will perform centralised assessment and reporting.

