7.2.4. Baseline and Change from Baseline

For all change from baseline variables, the baseline is defined as the last non-missing assessment prior to or on the day of randomization, and must be prior to the first administration of study treatment, including scheduled and unscheduled visits, unless otherwise specified. Hence, change from baseline = post-baseline value – baseline value.

The baseline value for analyses of qualitative parameters (e.g., normal/abnormal) is defined as the last evaluation prior to or on the day of randomization, and must be prior to the first administration of study treatment.

This document is confidential.

The baseline value for the PRO questionnaires and diary will be the average of the 7 days before starting study treatment.

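### SAP Appendix 1 closes the POEM and post-baseline diary windows the day before the visit, although the protocol has patient-reported outcomes completed at the start of the visit

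*SAP*

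**What the plan says.** **SAP Appendix 1** maps pruritus NRS and sleep loss to study weeks as a daily diary. Each window is the seven days ending the day before: the baseline row ends at "Date of First Injection-1" and the Week 16 row at "Week 16 Visit Date - 1". On POEM it says that "POEM are collected every week via eDiary", that "the evaluation window is injection date - 7 to injection date -1 for baseline", and that after baseline "the last collected POEM data before the visit date would be used". Its worked example takes a visit on the 14th and uses scales completed from the 7th to the 13th.

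**SAP 7.2.4** first gives a general rule: the last pre-dose assessment on or before the day of randomisation, unless specified otherwise. It then adds: "The baseline value for the PRO questionnaires and diary will be the average of the 7 days before starting study treatment".

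**Protocol 10.1** says: "PROs will be assessed at the start of the visit before any other assessments or procedures". The same section and Table 1 footnote d give PROs a window of -3 days in Induction and -5 days in Maintenance.

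**Protocol Table 1** schedules POEM and RECAP at Day 1 and Weeks 4, 8, 12 and 16 in Induction. DLQI/CDLQI, WHO-5 and TSQM-9 also start on Day 1, and none of the five is done at Screening. For pruritus, footnote j reads "To be performed daily up to W2, weekly from W2 to W16, and every 2 weeks from W16 onward". Footnote k gives sleep loss and skin pain the same pattern, but every 4 weeks after Week 16. The flowchart footnotes in SAP 4.6 repeat these timings.

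**The concern.** A window of days -7 to -1 costs little when entries are daily, because losing the visit-day entry still leaves seven scores. After Week 2 the collection is sparser than Appendix 1 assumes, and the excluded visit-day entry can be the only one that belongs to that visit.

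Three results are at stake. Change from baseline in POEM, a secondary endpoint, needs both a Day 1 value and a visit value. The 4-point pruritus response at Week 16, a key secondary endpoint, may rest on an entry from an earlier week. Maintenance pruritus and sleep-loss summaries may show missing values where the patient did answer. In each case the data are collected as the protocol asks and then set aside by a derivation rule.

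**Working it through.** **Rule.** An entry on day d, counted relative to the visit (day 0), is kept if -7 ≤ d ≤ -1.

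**Reproducing the SAP's example.** For a visit on the 14th, 14 - 7 = 7 and 14 - 1 = 13, so days 7 to 13 are kept and the 14th is not. This matches Appendix 1 and shows that leaving out the visit day is intended.

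**Permitted completion days.**
- Induction: -3, -2, -1, 0. Kept: -3, -2, -1, which is 3 of 4.
- Maintenance: -5 to 0. Kept: -5 to -1, which is 5 of 6.

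Only day 0 is lost in either period.

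**Entry made on the visit day.** The question is whether any other scheduled entry falls in days -7 to -1.

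| Scale and period | Previous scheduled entry | In the window? | Result |
|---|---|---|---|
| POEM, Day 1 | none | no | baseline missing |
| POEM, Weeks 4 to 16 | day -28 | no | visit value missing |
| Pruritus and sleep loss, weekly phase (e.g. Week 16) | day -7 | yes | earlier entry scored as this week |
| Pruritus, Maintenance | day -14 | no | missing |
| Sleep loss, Maintenance | day -28 | no | missing |
| Pruritus and sleep loss, Week 2 (daily phase) | days -7 to -1 | yes | seven scores, no problem |

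One entry in seven days is enough for a post-baseline weekly score, so Week 16 pruritus is missing only if the previous entry is absent or more than 7 days old.

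**Diary on fixed dates.** Suppose instead that weekly entries fall on nominal days 105 and 112 whatever the visit date. A Week 16 visit 0 to 3 days early (days 109 to 112) uses day 105. A visit 1 to 3 days late uses day 112.

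**Baselines.** Days -7 to -1 before first injection give up to seven daily scores for pruritus, sleep loss and skin pain. Protocol 10.4.5 and 10.4.7 define the pruritus and skin-pain baselines in this way, so the documents agree there. A questionnaire completed once on Day 1 has no seven-day series to average, and Day 1 itself lies outside the seven days before treatment.

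**With a window of visit -6 to visit.** All permitted days are kept: 4 of 4 in Induction and 6 of 6 in Maintenance. For weekly, 2-weekly and 4-weekly scales the visit-day entry is the one selected. In the fixed-date case only a visit exactly on day 112 changes, from the day-105 entry to the day-112 entry.

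**The case against.** Entries 1 to 3 days before the visit (1 to 5 in Maintenance) comply with the protocol and are kept. They are made in an app, usually on the patient's own phone, so early completion is realistic. The rule is the same in both blinded arms, and nothing here shows bias or loss of power on the pruritus endpoint. Closing the window at day -1 also guards against post-dose entries. Appendix 1 filters by date, not time, and at Week 16 the placebo arm receives active drug. All of this stands. The last point means that the visit day cannot simply be added without a pre-dose condition.

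Four stronger readings are tempting, but the documents do not support them.

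- **The Day 1 pruritus and skin-pain baselines are wrongly dropped.** They are not: the protocol itself puts these baselines on the preceding seven days.
- **Week 16 pruritus is generally lost to imputation.** With weekly spacing it is displaced by up to a week. It becomes missing only with irregular spacing or a skipped entry.
- **DLQI change cannot be computed.** Appendix 1 sets no post-baseline window for DLQI/CDLQI, RECAP, WHO-5 or TSQM-9. Their problem is one sentence in SAP 7.2.4, which conflicts with how they are collected. That sentence needs correcting, but it does not show that their visit scores are discarded.
- **25% to 100% of scores are lost.** The 25% assumes completion spread evenly over four permitted days, and the 100% assumes that everyone completes on the visit day. Neither is in the documents.

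**Conclusion.** The mismatch is in the text, and the SAP's own example confirms it. It is firmest for POEM: a form completed on Day 1 or on a visit day has no value in its window, so change from baseline is missing. In the weekly phase, a pruritus entry made on the Week 16 visit day is normally replaced by one from about a week earlier. In Maintenance, 2-weekly pruritus and 4-weekly sleep-loss entries made on the visit day become missing. The 7-day average baseline in SAP 7.2.4 does not fit POEM, RECAP, DLQI/CDLQI, WHO-5 or TSQM-9.

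The size depends on the share of entries made on the visit day. That share could lie anywhere from 0% to 100%, and the documents give no figure. The results above assume entries on the scheduled spacing. The primary endpoint is not affected. The point deserves correction because a key secondary endpoint and several secondary endpoints depend on these rules.

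**What to change.** 1. In Appendix 1, change the post-baseline pruritus, sleep-loss and POEM windows to visit date -6 through visit date. On the visit day, accept only entries made before dosing, identified by time stamp.
2. Leave the pruritus, sleep-loss and skin-pain baselines at days -7 to -1.
3. In SAP 7.2.4, limit the 7-day average baseline to those three diary scales. For POEM, RECAP, DLQI/CDLQI, WHO-5 and TSQM-9, use the last value on or before Day 1, pre-dose.
4. Align the stated POEM and diary frequencies with the Schedule of Assessments.

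The cost is SAP wording and a change to the window derivation program; no new data are needed. The documents do not say whether entry and dosing times are both recorded, so confirm this before finalising item 1.
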